4 STUDY DESIGN

4.1 Study Overview

Randomized, multi-site double-blind placebo-controlled trial of melatonin 3 mg vs. 6 mg vs. placebo. Randomization will be 1:1:1 in blocks of 6 by site. We will use a “remote trial” design, wherein after the initial in-person enrollment visit all study procedures will be done from the comfort of the participant’s own home.

We intend to enroll approximately 210 participants over 24-30 months at two sites: UCLA and UCSF. The duration of participation for each participant will be 4 months:

- 1) 8-week single-blind placebo treatment-phase
- 2) 8-week randomized treatment phase

5 CRITERIA FOR EVALUATION

5.1 Primary Efficacy Endpoint

1. Mean migraine/migrainous days in weeks 5-8 of randomized treatment phase in melatonin treated participants vs. placebo.

5.2 Secondary Efficacy Endpoints

1. Mean migraine/migrainous days in weeks 5-8 of randomized treatment phase in melatonin 6 mg vs. placebo.
2. Mean migraine/migrainous days in weeks 5-8 of randomized treatment phase in melatonin 3 mg vs. placebo.
3. Mean migraine/migrainous days in weeks 5-8 of randomized treatment phase in melatonin 6 mg vs. melatonin 3 mg.
4. Change in mean migraine/migrainous days from weeks 5-8 of single-blind treatment phase to weeks 5-8 of randomized treatment phase for each group.
5. Mean PedMIDAS (headache related disability score) in weeks 5-8 of randomized treatment phase in melatonin treated group vs placebo, and in each of the three pair-wise group comparisons.
6. Mean CASQ score in weeks 5-8 of randomized treatment phase in melatonin treated group vs. placebo, and in each of the three pair-wise group comparisons.
7. Number of days acute medication is used in weeks 5-8 of randomized treatment phase in melatonin treated group vs. placebo, and in each of the three pair-wise group comparisons.
8. Number of headache days in weeks 5-8 of randomized treatment phase in melatonin treated group vs. placebo, and in each of the three pair-wise group comparisons.

5.3 Safety Evaluations

1. Incidence of adverse events

6 SUBJECT SELECTION

6.1 Study Population

Subjects with a diagnosis of migraine who meet the inclusion and exclusion criteria will be eligible for participation in this study.

6.2 Inclusion Criteria

1. Age 10-17—inclusive
2. Weight ≥ 40 kg, so as not to require mg/kg based dosing
3. Meets International Classification of Headache Disorders III beta¹ criteria for migraine in children/adolescents (international standard diagnostic criteria for research)
4. Lives in the state of California- to allow shipping of study medication from our pharmacy
5. Has at least one parent who speaks English—in order to ensure good communication with study team by phone
6. Has daily access to a smartphone in order to provide daily headache diary data
7. A Parent/Guardian consents and the adolescent is cognitively capable of giving assent to participate
8. Either not on a migraine preventive medication, or if on one the dose has been stable for at least 4 weeks prior to enrollment, or are willing to wait to start the study until they have reached a stable dose for 4 weeks
9. Willing to not use OTC melatonin or change migraine preventives during the trial
10. Has ≥ 1 headache day per week, or 4-28 days of headache in a 28-day period
Episodic headaches have been present for a minimum of 6 months—This lowers the likelihood of a secondary cause of headaches

6.3 Exclusion Criteria

1. Continuous headache
2. History of seizures/epilepsy
3. Pregnant/lactating
4. Concomitant opioid or barbiturate overuse, wherein overuse is defined as ≥ 4 days per month of barbiturate containing compounds, ≥ 10 days per month of opioid containing compounds as these may impact sleepiness scales
5. If in the investigator's opinion there is a medical or psychiatric concern that makes them think the participant should not participate
6. Inability to swallow pills after teaching and practice
History of nocturnal asthma, as evidenced by a having a diagnosis of asthma and symptoms that manifest as nighttime awakening due to cough, wheeze, and/or shortness of breath

Randomization Criteria:

1. Had 4-28 migraine/migrainous days in the 28-day period of weeks 5-8 of single-blind placebo treatment phase, but not continuous headache.

2. At least 80% compliance with headache diary (i.e. at least 23 headache diary days) during weeks 5-8 of single-blind placebo treatment phase.

7 CONCURRENT MEDICATIONS

All subjects should be maintained on the same medications throughout the entire study period, as medically feasible, with no introduction of new preventive therapies.

7.1 Allowed Medications and Treatments:

As stated in the exclusionary criteria above, subjects can use their usual acute headache medications as long as there is not medication overuse (defined above). All other medications are acceptable.

7.2 Prohibited Medications and Treatments:

Overuse of acute headache medications, wherein medication overuse is defined as ≥ 4 days per month of barbiturate containing compounds and/or ≥ 10 days per month of opioid containing compounds.

8 STUDY TREATMENTS

8.1 Method of Assigning Subjects to Treatment Groups

Randomization: 1:1:1 to melatonin 3 mg: 6 mg: placebo. Randomization will be done in blocks of 6 by site. A computer-generated scheme will be used to generate the randomization.

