10 EVALUATIONS BY VISIT

10.1 Visit 1 (Screening and Enrollment, Day 1)

We will do a one-time enrollment visit at either UCSF or UCLA.

Consent/assent: At the start of an enrollment visit, potential subjects and their parent/guardian will be told about the study by a study investigator and/or study coordinator and will be provided with an informed consent document to review. For 12-17 year-olds, the informed consent document is addressed to the adolescent and is to be signed by both the adolescent and their parent/guardian. For 10-11 year-olds, the parent will sign the consent form and the participant will be provided with a simplified assent document. For this group the participant's assent will be documented by a study team member. Participants and parents/guardians will be given the opportunity to ask questions and have them answered to their satisfaction before deciding whether to participate. Consent and HIPPA can be signed with paper/pen or via DocuSign.

Enrollment visit data:

The enrollment visit data will be entered directly into the study database during the enrollment visit. Demographic and logistical information will be collected including name, age, sex, race/ethnicity, shipping address, participant smartphone number, parent smartphone number, and best times for follow-up calls. A pediatric headache neurologist will review the headache history to ensure the participant meets ICHD criteria for migraine with or without aura and will review the current medication list and past medical history. We will measure weight, blood pressure, pulse, and respiratory rate. There will be a general medical examination and a neurologic examination. Girls who have had their first period will undergo a urine pregnancy test. Baseline assessment of the PedMIDAS score and CASQ score will be assessed. Participants will be taught how to use the headache diary on their smartphone. They will be given the study medication for the single-blind placebo treatment phase and instructed to take study medication 1 hour before bedtime.

10.2 8-week single-blind placebo treatment phase (Weeks 1-8):

Participants will take the study medication nightly and complete a headache diary nightly. A text message will be sent from the study database each evening to remind them to do

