these two tasks, and to provide a link to their headache diary. If they do not complete the headache diary, a reminder text will be sent the next morning. If they do not complete the headache diary for three days in a row, a study staff member will call to check in and remind them to do it and answer any questions. There will be a scheduled check in call at the four-week mark and again at the 8-week mark. If they provide headache diary data on $\geq 80\%$ of days in each 28-day period, they will receive a \$5 gift card each month. Once they have completed the 8-weeks of placebo treatment, they will return their study medication in a self-addressed envelope via FedEx.

10.3 Assessment of randomization eligibility (Day 57):

If the participant meets randomization criteria, the study pharmacy (Safeway) will be notified by study staff and the study pharmacy will review the randomization scheme to assign treatment and will enter this data into the study database. The study medication will be shipped to the participant's shipping address via FedEx.

Study staff will track the shipment via FedEx's tracking number on their website. Once the package shows as delivered, study staff will enter this information into the study database and a text message will be sent to the parent's smartphone asking them to confirm receipt of the study medication. The date the parent confirms receipt of the study medication will be day 1 of the randomized treatment phase.

10.4 8-week randomized treatment phase (Weeks 9-16):

Participants will take the study medication nightly and complete a headache diary nightly. A text message will be sent from the study database each evening at 9:00 PM to remind them to do these two tasks, and to provide a link to their headache diary. If they do not complete the headache diary, a reminder text will be sent the next morning. If they do not complete the headache diary for three days in a row, a study staff member will call to check in and remind them to do it and answer any questions. There will be a scheduled check in call at the four-week mark and again at the 8-week mark. If they provide headache diary data on $\geq 80\%$ of days in each 28-day period, they will receive a \$5 gift card each month. Once they have completed the 8-weeks of treatment, they will return their study medication in a self-addressed envelope via FedEx.

10.5 Study completion (Day 113):

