14.3 Analysis of Primary Endpoint

Primary outcome: Number of migraine/migrainous days in the 5th-8th weeks of randomized treatment between melatonin (combined 6 mg+3mg) vs. placebo. We will control for baseline migraine/migrainous day frequency in the 5-8th week of the single-blind treatment phase and use an ANCOVA analysis.

Definition of migraine/migrainous day:

- 1) Patient had a moderate or severe headache and took a migraine-specific medication (triptan or ergot)
- 2) Patient had a moderate or severe headache; headache lasted for at least 2 hours, and
 - a. At least one of the following was present (throbbing quality, movement sensitivity, or unilateral/bilateral location) AND
 - b. At least one of the following was also present (photophobia, phonophobia, nausea or vomiting)

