14.4 Analysis of Secondary Endpoints

Secondary outcome measures will include $\geq 50\%$ responder rates, tolerability (as measured by CASQ scores), and need for use of acute headache medications. Safety and tolerability data will be summarized by treatment group. Adverse event rates will be coded by body system. Adverse events will be tabulated by treatment group and will include the number of patients for whom the event occurred, the rate of occurrence, and the severity and relationship to study drug.

Secondary outcomes:

(We will control for the baseline level of these outcomes in all of these analyses)

Effectiveness secondary outcomes:

1. Number of migraine/migrainous days in the 5th-8th weeks of randomized treatment between **melatonin 3 mg vs. placebo**.

2. Number of migraine/migrainous days in the 5th-8th weeks of randomized treatment between **melatonin 6 mg vs. placebo**.
3. Number of migraine/migrainous days in the 5th-8th weeks of randomized treatment between **melatonin 3 mg vs. 6 mg**.
4. Mean headache days in 5th-8th randomized phase in melatonin (combined) vs. placebo, (followed by melatonin 3 mg vs. placebo, melatonin 6 mg vs. placebo, and melatonin 3 mg vs. melatonin 6 mg using t-tests).
5. Mean acute medication use days in 5th-8th randomized phase in melatonin (combined) vs. placebo, (followed by melatonin 3 mg vs. placebo, melatonin 6 mg vs. placebo, and melatonin 3 mg vs. melatonin 6 mg using t-tests).
6. Mean PedMIDAS score (continuous) in 5th-8th randomized phase in melatonin (combined) vs. placebo, (followed by melatonin 3 mg vs. placebo, melatonin 6 mg vs. placebo, and melatonin 3 mg vs. melatonin 6 mg using t-tests).
7. $\geq 50\%$ responder rate in 5th-8th randomized phase in melatonin (combined) vs. placebo (Chi-square or Fisher's exact (if needed), (followed by melatonin 3 mg vs. placebo, melatonin 6 mg vs. placebo, and melatonin 3 mg vs. melatonin 6 mg using Chi-square (or Fisher's exact)).

Safety outcomes:

1. Proportion with adverse events between groups
 - a. Proportion with serious adverse events between groups
 - b. Proportion of adverse events thought to be related to the study treatment
2. Mean Sleepiness score in 5th-8th randomized phase in melatonin (combined) vs. placebo, (followed by melatonin 3 mg vs. placebo, melatonin 6 mg vs. placebo, and melatonin 3 mg vs. melatonin 6 mg using t-tests).

Trial design assessment outcome:

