14.6 Sample Size and Randomization

To detect a difference of 1.1 migraine/migrainous days (SD 1.8) between groups, as was seen in the adolescent topiramate migraine prevention trial that led to FDA-approval of that agent in 12-17 year-olds, we need outcome data on 42 participants/arm. We anticipate that 25% of enrolled participants will be screened out by the single-blind placebo run-in process, and that 85% of those who randomize will complete the trial. Therefore we will enroll 70 per arm, or $n=210$ total.

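### Randomisation is blocked by site, but no planned analysis includes site; the cost is a small, conditional loss of precision that one model term removes

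*Combined protocol and SAP*

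**What the plan says.** Section 4.1 sets out the allocation: "Randomization will be 1:1:1 in blocks of 6 by site". Section 8.1 repeats the blocking: "Randomization will be done in blocks of 6 by site". The two sites are UCSF and UCLA.

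For the primary endpoint, Section 14.3 says: "We will control for baseline migraine/migrainous day frequency in the 5-8th week of the single-blind treatment phase and use an ANCOVA analysis". The synopsis and Section 3.1 name the same single covariate. For the secondary outcomes, Section 14.4 says: "We will control for the baseline level of these outcomes in all of these analyses". It names t-tests and chi-square or Fisher's exact tests for the comparisons.

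Nothing in Section 14 puts site in a model, stratifies a test by site, or explains why site is left out. On sample size, Section 14.6 says "we need outcome data on 42 participants/arm" to detect 1.1 days with SD 1.8.

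**The concern.** Blocking within site keeps the arms balanced at each site, so a difference in outcome level between sites drops out of the treatment comparison. The true sampling variance of the treatment effect then depends only on within-site variation.

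An analysis that ignores site estimates the residual variance from all participants together. Any site difference that the baseline covariate has not absorbed is counted there as noise. The reported standard error exceeds the true one, the confidence interval is too wide, and the test rejects less often than its nominal level. A site difference that baseline does absorb does no harm.

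What is at stake is precision, not validity: the design pays for stratification and the analysis does not collect the return. The single-dose comparisons, which come first among the secondary objectives, have less power to spare than the pooled contrast.

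**Working it through.** **Inputs from the documents.** Difference 1.1 days, SD 1.8, 42 evaluable per arm (Section 14.6). Allocation 1:1:1 (Section 8.1), so the primary contrast is 84 against 42.

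**Assumptions.** The documents do not give these:
- two-sided 5% test;
- sites of equal size (a 70/30 split is also shown);
- 1.8 is the within-site residual SD (the total-SD reading is also shown);
- site gap remaining after baseline adjustment of 0.5, 1, 1.5 or 2 days. The last two exceed the 1.1-day target effect and only bound the range.

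**Step 1: the plan's own figure.** With two-sided 5% and 80% power, n per arm = 2 × (1.960 + 0.842)² × (1.8/1.1)² = 42.03. This agrees with the stated 42, so the assumed error rates fit the plan.

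**Step 2: true standard error under blocking.**
- Pooled melatonin vs placebo: 1.8 × √(1/84 + 1/42) = 0.340
- One dose vs placebo: 1.8 × √(2/42) = 0.393

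**Step 3: standard error reported without site.** With a share p of participants at one site, the residual SD becomes √(1.8² + p(1−p) × gap²). For equal sites and a 1-day gap this is √(3.24 + 0.25) = 1.868, and 1.868/1.8 = 1.038, so the standard error is overstated by 3.8%.

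**Step 4: power and type I error.** Power is taken from the noncentral t distribution, with the critical value multiplied by the inflation from Step 3. Power with site in the model is 89.40% (pooled) and 79.01% (one dose).

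| Assumed residual site gap (days) | 0.5 | 1 | 1.5 | 2 |
|---|---|---|---|---|
| SE overstated (%) | 1.0 | 3.8 | 8.3 | 14.4 |
| Pooled 95% half-width, days (0.673 with site) | 0.680 | 0.699 | 0.73 | 0.770 |
| Pooled: actual type I error (%) | 4.8 | 4.2 | 3.4 | 2.5 |
| Pooled: power lost (points) | 0.35 | 1.43 | 3.33 | 6.16 |
| Pooled, 70/30 sites: power lost | 0.29 | 1.20 | 2.77 | 5.10 |
| One dose vs placebo: power lost | 0.54 | 2.21 | 5.04 | 9.05 |

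**Step 5: 1.8 read as the total SD.** The within-site SD is then √(1.8² − gap²/4). Pooled power without site is 89.6 / 90.3 / 91.5 / 93.3% over the four gaps, and with site 90.0 / 91.6 / 94.2 / 97.1%. Nothing is lost against plan, but a gain of 0.3 / 1.3 / 2.7 / 3.9 points is forgone.

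**Step 6: cost of the term if there is no gap.** Pooled power is 89.41% without site and 89.40% with it. For one dose the figures are 79.02% and 79.01%.

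**Step 7: simulation.** With 126 completers (sites of 66 and 60), permuted blocks of 6 and 12,000 runs per setting, pooled power over the four gaps was 88.5 / 87.4 / 85.9 / 82.7% without site and 88.9 / 88.9 / 89.1 / 89.1% with it. Type I error without site was 5.1 / 4.3 / 3.3 / 2.5%. These agree with Step 4 within simulation error.

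**The case against.** The strongest reply is that the effect is probably negligible.

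- **No site gap is documented, and the design points to a small one.** Section 4.1 says that "after the initial in-person enrollment visit all study procedures will be done from the comfort of the" participant's own home. Diary, pharmacy and eligibility rules are common to both sites, and baseline is measured over a matching 28-day window. This stands: the low end of the range is the realistic one, and the 1.5- and 2-day columns should carry little weight.
- **The plan has some margin.** Section 14.6 enrols 70 per arm, so 70 × 0.75 × 0.85 = 44.6 evaluable are expected. At that number pooled power with site is 91.1%, and the losses at 0.5 and 1 day are 0.31 and 1.26 points. One dose against placebo has 81.4% with site, and still 79.4% with a 1-day gap and no site term. This stands too.
- **The residual SD may exceed 1.8**, because participants with 4 to 28 days are admitted. If it were 3, 4 or 5 (assumed values), the pooled loss at a 1-day gap would be 1.07, 0.53 or 0.28 points. This is fair, although it lowers power generally.
- **Dropout and incomplete blocks loosen the balance.** In simulations with about 16% dropout, type I error at a 2-day gap was about 3.1 to 3.3%, not 2.5%. So Step 4 somewhat overstates the conservatism at large gaps. The power loss remained, at about 0.4 / 1.6 / 7 points for gaps of 0.5 / 1 / 2 days.

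None of this gives a reason to leave site out. It bears on how much is gained by including it.

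**Conclusion.** The point holds, at low severity. Site is a randomisation stratum that no planned analysis uses. If the sites differ after baseline adjustment, the reported standard errors are too large. The realistic cost to the primary contrast is about 0.35 to 1.4 points of power for gaps of 0.5 to 1 day, and 0.5 to 2.2 points for a single dose against placebo. If there is no residual gap, the cost is zero.

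These sizes rest on the assumed gaps, a two-sided 5% test, near-equal sites and 1.8 as the within-site SD. The direction does not depend on those values. There is no bias, no inflated false-positive rate and no sample-size error, so the trial's conclusion is not threatened. The case for acting is that the remedy is almost free, and that writing it down now settles the question of site before unblinding.

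**What to change.** State in Section 14.3 that the primary ANCOVA is: weeks 5–8 migraine/migrainous days ~ arm (combined melatonin vs placebo) + baseline migraine/migrainous days + site, with site as a fixed two-level factor.

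In Section 14.4, include site alongside the baseline control already promised for the secondary comparisons. For the responder rate, a site-adjusted analysis (for example logistic regression with baseline and site) is optional, because the gain is small.

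The cost is one degree of freedom and minor analysis work. No new data are needed. Section 10.1 says "We will do a one-time enrollment visit at either UCSF or UCLA", so each participant's site is known. Section 10.3 says that "the study pharmacy will review the randomization scheme to assign treatment and will enter this data into the study database", and that scheme is the site-blocked one.

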8.2 Blinding

Due to the objectives of the study, the identity of test and control treatments will not be known to investigators, research staff, or patients. The two melatonin doses and the placebo will be indistinguishable in terms of color, appearance, taste, and smell.

During the study, the blind may be broken **only** in emergencies when knowledge of the patient's treatment group is necessary for clinical patient management.

The study blind will be broken on completion of the clinical study and after the study database has been locked.

8.3 Formulation of Test and Control Products

8.3.1 Formulation of Test Product

The drug product is a commercial melatonin 3 mg tablet that is lawfully marketed in the U.S. by Nature's Bounty. The commercial label is attached to this application. For the purpose of blinding, Safeway Pharmacy will over-encapsulate the tablets using a microcrystalline cellulose filler. We will not make any other changes of any kind to the finished marketed Nature's Bounty melatonin product. We do not think that overencapsulating this melatonin product will effect absorption and we have discussed this with the study pharmacist. While it is possible that absorption will be somewhat slower than with the under the tongue method, we do not think this is problematic as we

do not think speed of absorption of melatonin will have a role in its efficacy as a migraine preventive.

Those assigned to placebo will take 1 placebo capsule nightly. Those assigned to melatonin 3 mg will take one capsule nightly (will contain 1 x 3 mg tablet). Those assigned to melatonin 6 mg will take 1 capsule nightly (will contain 2 x 3 mg tablets).

| | Study Drug | Placebo |
|--------------------------|--|----------------------------|
| Active Ingredient, mg/mL | 3.36mg melatonin (as per labdoor.com analysis—attached) | N/A |
| Other ingredient, mg/mL | Mannitol, Crospovidone, Vegetable Stearic Acid, Natural Cherry Flavor, Beet Juice Color, Malic Acid, Sucralose, Vegetable Magnesium Stearate, Microcrystalline cellulose | Microcrystalline cellulose |

